7.2 Laboratory Procedures/Evaluations

7.2.1

Clinical Laboratory Evaluations

Not applicable.

7.2.2

Other Assays or Procedures

Not applicable.

7.2.3

Specimen Preparation, Handling, and Storage

Not applicable.

7.2.4

Specimen Shipment

Not applicable.

7.3 Study Schedule

All of the visits described below are part of the research study. Study participants are still part of the school-based caries prevention program at the same time.

7.3.1

Screening

Screening (Day -28 to -1)

- Obtain informed consent of potential participant verified by signature on written informed consent for screening form.
- Review medical history to determine eligibility based on inclusion/exclusion criteria.
- Review dental history to determine eligibility based on inclusion/exclusion criteria.
- Schedule study visits for participants who are eligible and available for the duration of the study.

7.3.2

Enrollment/Baseline

Enrollment/Baseline Visit (Visit 1, Day 0)

- Obtain informed consent of potential participant, if not obtained in Screening period
- Verify inclusion/exclusion criteria.
- Perform comprehensive oral examination
- Administer the study treatment following first-stage randomization (See Figure 1):
 - Either silver diamine fluoride or glass ionomer cement sealants

7.3.3

Intermediate Visits

7.3.3.1 Visit 2

(Day 160-200)

- Record adverse events as reported by participant or observed by investigator.
- Perform comprehensive oral examination
- Record patients responsiveness status
- Proceed with second stage randomization if determined by comprehensive examination to be in treatment nonresponse (See Figure 1)
- Administer relevant treatment as indicated by second stage randomization

7.3.3.2 Visit 3

(Day 340-380)

- Record adverse events as reported by participant or observed by investigator.
- Perform comprehensive oral examination

- Record patients responsiveness status
- Proceed with second stage randomization if determined by comprehensive examination to be in treatment nonresponse (See Figure 1)
- Administer relevant treatment as indicated by second stage randomization

7.3.3.3 Visit 4

(Day 520-560)

- Record adverse events as reported by participant or observed by investigator.
- Perform comprehensive oral examination
- Document clinical outcomes
- Maintain treatment as indicated in Subgroup (Figure 1)

7.3.3.4 Visit 5

(Day 700-740)

- Record adverse events as reported by participant or observed by investigator.
- Perform comprehensive oral examination
- Record patients responsiveness status
- Document clinical outcomes
- Maintain treatment as indicated in Subgroup (Figure 1)

7.3.4

Final Study Visit

Final Study Visit (Visit 6, Day 880-920)

- Record adverse events as reported by participant or observed by investigator.
- Perform comprehensive oral examination
- Record patients responsiveness status
- Document clinical outcomes
- Provide all participants with any needed care (dental sealants on sound dentition, ART or SMART on any carious posterior dentition, in accordance with Figure 1)

7.3.5

Withdrawal/Early Termination Visit

If the patient is willing, a final comprehensive exam will be provided if a subject withdraws from the study.

7.3.6

Unscheduled Visit

There are no unscheduled visits.

7.4 Concomitant Medications, Treatments, and Procedures

Concomitant medications are not applicable. However, concomitant treatments and procedures that are observed through oral examinations (e.g., care provided by an external dentist, such as evidence of teeth with fillings that were not observed previously) will be noted in EHRs.

7.5 Justification for Sensitive Procedures

Not applicable.

7.5.1

Procedures

Precautionary Medications, Treatments, and

Not applicable.

7.6 Prohibited Medications, Treatments, and Procedures

Not applicable.

7.7 Prophylactic Medications, Treatments, and Procedures

Dental sealants, silver diamine fluoride, and fluoride varnish are preventive care.

7.8 Rescue Medications, Treatments, and Procedures

Should children experience caries are treatment with SDF or dental sealants, we will provide SDF (for caries management), atraumatic restorations, or silver modified atraumatic restorative treatment.

7.9 Participant Access to Study Agent at Study Closure

Not applicable.

8 Assessment of Safety

8.1 Specification of Safety Parameters

All interventions provided in this study are standard of care; there are no safety parameters that are study endpoints. Any adverse events experienced will be recorded in patient electronic health records and reported according to the guidelines described in Section 8.

8.1.1 Definition of Adverse Events (AE)

An **adverse event** (AE) is any symptom, sign, illness or experience that develops or worsens in severity during the course of the study. Intercurrent illnesses or injuries should be regarded as adverse events. Abnormal results of diagnostic procedures are considered to be adverse events if the abnormality:

- results in study withdrawal
- is associated with a serious adverse event
- is associated with clinical signs or symptoms
- leads to additional treatment or to further diagnostic tests
- is considered by the investigator to be of clinical significance

8.1.2 Definition of Serious Adverse Events (SAE)

Serious Adverse Event

Adverse events are classified as serious or non-serious. A **serious adverse event** is any AE that is:

- fatal
- life-threatening
- requires or prolongs hospital stay
- results in persistent or significant disability or incapacity
- a congenital anomaly or birth defect
- an important medical event

Important medical events are those that may not be immediately life threatening, but are clearly of major clinical significance. They may jeopardize the subject, and may require intervention to prevent one of the other serious outcomes noted above. For example, drug overdose or abuse, a seizure that did not result in in-patient hospitalization, or intensive treatment of bronchospasm in an emergency department would typically be considered serious.

All adverse events that do not meet any of the criteria for serious should be regarded as **non-serious adverse events**.

8.1.3 Definition of Unanticipated Problems (UP)

Unanticipated Problems Involving Risk to Subjects or Others

Any incident, experience, or outcome that meets all of the following criteria:

- Unexpected in nature, severity, or frequency (i.e. not described in study-related documents such as the IRB-approved protocol or consent form, the investigators brochure, etc)
- Related or possibly related to participation in the research (i.e. possibly related means there is a reasonable possibility that the incident experience, or outcome may have been caused by the procedures involved in the research)
- Suggests that the research places subjects or others at greater risk of harm (including physical, psychological, economic, or social harm).

8.2 Classification of an Adverse Event

8.2.1 Severity of Event

For AEs not included in the protocol defined grading system, the following guidelines will be used to describe severity.

- **Mild** – Events require minimal or no treatment and do not interfere with the participant's daily activities.
- **Moderate** – Events result in a low level of inconvenience or concern with the therapeutic measures. Moderate events may cause some interference with functioning.
- **Severe** – Events interrupt a participant's usual daily activity and may require systemic drug therapy or other treatment. Severe events are usually potentially life-threatening or incapacitating.

8.2.2 Relationship to Study Agent

For all collected AEs, the clinician who examines and evaluates the participant will determine the AE's causality based on temporal relationship and his/her clinical judgment. AE's will be classified on the following criteria:

- **Related** – The AE is known to occur with the study agent, there is a reasonable possibility that the study agent caused the AE, or there is a temporal relationship between the study agent and event. Reasonable possibility means that there is evidence to suggest a causal relationship between the study agent and the AE.
- **Not Related** – There is not a reasonable possibility that the administration of the study agent caused the event, there is no temporal relationship between the study agent and event onset, or an alternate etiology has been established.

8.2.3 Expectedness

PI [name] and Medical Monitor [name] will be responsible for determining whether an AE is expected or unexpected. An AE will be considered unexpected if the nature, severity, or frequency of the event is not consistent with the risk information previously described for the study agent.

8.3 Time Period and Frequency for Event Assessment and Follow-Up

The occurrence of an AE or SAE may come to the attention of study personnel during study visits and interviews of a study participant presenting for medical care, or upon review by a study monitor. All AEs including local and systemic reactions not meeting the criteria for SAEs will be captured on the appropriate RF. Information to be collected includes event description, time of onset, clinician's assessment of severity, relationship to study product (assessed only by those with the training and authority to make a diagnosis), and time of resolution/stabilization of the event. All AEs occurring while on study must be documented appropriately regardless of relationship. All AEs will be followed to adequate resolution.

Any medical condition that is present at the time that the participant is screened will be considered as baseline and not reported as an AE. However, if the study participant's condition deteriorates at any time during the study, it will be recorded as an AE. UPs will be recorded in the data collection system throughout the study.

Changes in the severity of an AE will be documented to allow an assessment of the duration of the event at each level of severity to be performed. AEs characterized as intermittent require documentation of onset and duration of each episode.

The PI will record all reportable events with start dates occurring any time after informed consent is obtained until 7 (for non-serious AEs) or 30 days (for SAEs) after the last day of study participation. At each study visit, the investigator will inquire about the occurrence of AE/SAEs since the last visit. Events will be followed for outcome information until resolution or stabilization.

All unresolved adverse events should be followed by the investigator until the events are resolved, the subject is lost to follow-up, or the adverse event is otherwise explained. At the last scheduled visit, the investigator should instruct each subject to report any subsequent event(s) that the subject, or the subject's personal physician, believes might reasonably be related to participation in this study. The investigator should notify the study sponsor of any death or adverse event occurring at any time after a subject has discontinued or terminated study participation that may reasonably be related to this study. The sponsor should also be notified if the investigator should become aware of the development of cancer or of a congenital anomaly in a subsequently conceived offspring of a subject that has participated in this study.

8.4 Reporting Procedures – Notifying the IRB

8.4.1 Adverse Event Reporting

Adverse events will be reported regardless of the relationship to the study interventions to the IRB within the required timeframe for adverse event reporting as specified in the IRB Reportable Events Guidelines for required timeframe for reporting to the IRB.

8.4.2 Serious Adverse Event Reporting

SAEs that are unanticipated, serious, and possibly related to the study intervention will be reported to the IRB and PCORI in accordance with requirements:

- Unexpected fatal or life-threatening AEs related to the intervention will be reported to the Medical Monitor within 3 days of the investigator becoming aware of the event. Other serious and unexpected AEs related to the intervention will be reported within 7 days.
- Anticipated or unrelated SAEs will be handled in a less urgent manner but will be reported to the IRB in accordance with their requirements and will be reported to NIH on an annual basis.
- All other AEs documented during the course of the trial will be reported to NIH on an annual basis by way of inclusion in the annual report and in the annual AE/DSMP summary which will be provided to NIH.

We note that no clinical adverse events are expected.

8.4.3 Unanticipated Problem Reporting

Any incidents or events that meet the OHRP criteria for UPs will result in the creation and completion of an UP report form. The site investigator will report UPs to the IRB and to the NIMHD. Each UP report will include:

- Protocol identifying information: protocol title and number, PI's name, and the IRB project number;
- A detailed description of the event, incident, experience, or outcome;
- An explanation of the basis for determining that the event, incident, experience, or outcome represents an UP;
- A description of any changes to the protocol or other corrective actions that have been taken or are proposed in response to the UP.

To satisfy the requirement for prompt reporting, UPs will be reported using the following timeline:

- UPs that are SAEs will be reported to the IRB and to the NIMHD within 7 day of the investigator becoming aware of the event.
- Any other UP will be reported to the IRB and to the NIMHD within 15 days of the investigator becoming aware of the problem.
- All UPs should be reported to appropriate institutional officials (as required by an institution's written reporting procedures), the supporting agency head (or designee), and OHRP within 7 days of the IR's receipt of the report of the problem from the investigator.

8.4.4

Reporting of Pregnancy

Not applicable.

8.6 Reporting Procedures – Notifying the FDA

Any study event associated with the included medical devices in this study will be reported to the FDA. All events must be associated with the use of the device and unexpected. Any event that is fatal or life-threatening will be reported in 7 calendar days, and any that are serious but not fatal or live threatening, or a previous adverse event that was not initially deemed reportable but is later found to fit the criteria for reporting, will be reported within 15 calendar days.

8.7 Study Halting Rules

Given the 30-year history of the study investigators, we know of no safety issues that would prompt suspension of enrollment or the interventions. However, if we encounter serious, unexpected, and related AEs, the PIs, PCORI, and the IRB would confer to determine whether findings might trigger a safety review based on the number of overall SAEs, the occurrence frequency of the type of SAE, severe AEs/reactions, or increased frequency of events. There are no stopping rules needed for this study.

8.8 Safety Oversight

It is the responsibility of the Principal Investigator to oversee the safety of the study at each site. This safety monitoring will include careful assessment and appropriate reporting of adverse events as noted above, as well as the construction and implementation of a site data and safety-monitoring plan. Medical monitoring will include a regular assessment of the number and type of serious adverse events. An independent medical monitor will be appointed. The PI and sub-investigator [name] are responsible for data safety monitoring reviews. This includes conducting systematic and periodic reviews of aggregate data and adverse events. These specific data and events include staining due to silver diamine fluoride or allergic reaction to fluoride varnish. These data and events will be reviewed quarterly. These reviews will be disseminated to sites via email.

9 Clinical Monitoring

Clinical site monitoring is conducted to ensure that the rights and well-being of human subjects are protected, that the reported trial data are accurate, complete, and verifiable, and that the conduct of the trial is in compliance with the currently approved protocol/amendment(s), with GCP, and with applicable regulatory requirement(s).

- The clinical monitor, who is a licensed, board-certified pediatric dentist with experience implementing clinical research studies for school-based oral health programming, will conduct the monitoring on-site during annual trainings and assessments typically taking place during either the first two weeks of the academic school year, or the first two weeks of the Spring semester. Training will be comprehensive in nature to reflect fidelity to study intervention protocols, including data acquisition, clinical compliance, infection control, and data security, and be complimented by the authoring of quality assessment and improvement reports for review by the PI.
- Chairside audits will be conducted by the clinical monitor to ensure monitoring practices are performed consistently by all participating study personnel.
- Each clinical site will perform internal quality management of study conduct, data collection, documentation and completion. An individualized quality management plan will be developed to describe a site's quality management.

10 Statistical Considerations

10.1 Statistical and Analytical Plans (SAP)

A formal SAP will be completed prior to database lock and logged with the IRB.

10.2 Statistical Hypotheses

The null hypothesis is that there is no difference in treatment nonresponse between first stage assignments (SDF compared to dental sealants). The alternative hypothesis is that they are different. The study is a superiority trial. Endpoints will be evaluated at the end of the treatment nonresponse observational window (Study visit 3) and at the completion of subsequent visits (Study visit 4, 5, and 6).

10.3 Analysis Datasets

Analytic datasets will include intention-to-treat (all randomized participants) and per-protocol (those who completed enough visits sufficiently to ensure the full time for nonresponse has been observed, through third visit)

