6.3.3 Assessment of Clinician and/or Participant Compliance with Study Procedural Intervention

There is no assessment of participant compliance, as all treatments are provided by the school-based caries prevention program. Clinician compliance will be assessed by comparing the de-identified electronic health record data with the corresponding pathway from the research design. Any evidence of mis-match between what patients should have received and actually received will be recorded, noted in study notebooks, and communicated to the school-based caries prevention program.

7 Study Procedures and Schedule

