10.4 Description of Statistical Methods

10.4.1

General Approach

BASICS is a phase-III Sequential, Multiple Assignment, Randomized Trial (SMART) (described fully in the Schematic of Study Design). Descriptive statistics will use percentages and counts for persons with dichotomous outcomes and means/standard deviations for continuous outcomes. For inferential tests, the p-value used for statistical significance (Type 1 error) is 0.05, and all tests are two-tailed.

10.4.2

Analysis of the Primary Efficacy Endpoint(s)

The primary efficacy endpoints include the best initial treatment for dental caries and the best treatment sequence for nonresponders. This is equivalent to the main effect of the first-stage treatment and additional clinically-relevant contrasts (see Statistical Analysis Plan for further description). Data will be analyzed according to intent to treat. The main effects will be assessed using generalized linear mixed logistic regression (for presence/absence of dental caries and presence/absence of treatment nonresponse) and negative binomial regression (for caries incidence). Predictors include semester of entry, the interaction between semester and treatment trajectory, and any relevant demographic variables. Any instance of missing data will be accounted for using time-ordered nested conditional imputation.

10.4.3

Analysis of the Secondary Endpoint(s)

Secondary endpoints in BASICS include the best dynamic treatment regime, the optimal adaptive intervention, and costs of adaptive interventions. Analysis for the best adaptive intervention will utilize weighting and replication and other methods (see Statistical Analysis Plan). Analyses for identifying the optimal adaptive intervention will use Q-Learning (see SAP).

For cost analyses, we will quantify the economic costs of dynamic treatment regimes in school-based caries prevention will using microcosting in tandem with time studies. We will take a bottom-up microcosting approach to data collection. The bottom-up approach to microcosting is characterized by quantifying resource utilization for each cost item, and then aggregating to the individual or system-level, as opposed to assessing system costs and then allocating to individual cost items (top-down approach).⁷³ This approach is more accurate for labor-intensive services than microcosting with a top-down approach.⁷⁴⁻⁷⁶ We will use the following tools to capture costs:

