10.4.5 Adherence and Retention Analyses

As all treatments in this study are directly provided by a clinician to the patient, there is no measure of adherence to the protocol. However, we will provide descriptive statistical information of the number of patients lost to follow-up or changed schools within the study. Where possible, we will attempt to ascertain the reasons for discontinuation of the study, however in our experience in pragmatic school-based trials this usually stems from participants leaving the school district.

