14.3 Protocol Deviations

A protocol deviation is any noncompliance with the clinical trial protocol, GCP, or Manual of Procedures (MOP) requirements. The noncompliance may be either on the part of the participant, the investigator, or the study site staff. As a result of deviations, corrective actions are to be developed by the site and implemented promptly.

These practices are consistent with ICH E6:

- 4.5 Compliance with Protocol, sections 4.5.1, 4.5.2, and 4.5.3
- 5.1 Quality Assurance and Quality Control, section 5.1.1
- 5.20 Noncompliance, sections 5.20.1, and 5.20.2.

The PI and co-investigators will endeavor to identify and report deviations within 5 working days of identification of the protocol deviation, or within 5 working days of the scheduled protocol-required activity. All protocol deviations will subsequently be reported to the NYU Langone IRB.

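### Section 10.3 defines the per-protocol set by attendance through Visit 3 alone, so it is a completer set that keeps children treated off their assigned pathway

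*Protocol*

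**What the plan says.** Section 10.3 names two analysis sets. The first is "intention-to-treat (all randomized participants"). The second, called per-protocol, is "those who completed enough visits sufficiently to ensure the full time for nonresponse has been observed", up to the third visit. Nothing else is required for membership: no condition on first-stage treatment received, second-stage treatment received, eligibility or deviations.

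Other sections bear on it:

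- Section 6.3.3 sets up a fidelity check: "Clinician compliance will be assessed by comparing the de-identified electronic health record data with the corresponding pathway from the research design". It adds: "Any evidence of mis-match between what patients should have received and actually received will be recorded". The same section says that participant compliance is not assessed.
- Section 10.4.5 says that, because clinicians deliver every treatment, "there is no measure of adherence to the protocol". It plans descriptive statistics on loss to follow-up and school changes only.
- Section 14.3 takes a broad view of deviations, including those by site staff: "A protocol deviation is any noncompliance with the clinical trial protocol, GCP, or Manual of Procedures (MOP) requirements". Section 10.3 does not use it.
- Section 10.4.2 fixes the set for the primary analysis: "Data will be analyzed according to intent to treat". Section 10.2 calls the trial a superiority trial, with endpoints at Visits 3, 4, 5 and 6.

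**The concern.** A per-protocol set normally holds the participants who were treated as the protocol intended. The set in 10.3 selects only on whether the child was seen. It therefore adds selection on a post-randomization event, attendance, and does not do what its label promises, which is to set aside children who did not receive what they were assigned.

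Mismatches are plausible here. Clinicians are unmasked (10.6.1), one program delivers all the study treatments (7.1), and Section 2.4.1 accepts that the randomized treatment may differ from what a dentist would have chosen. At stake is the meaning of any result reported under the per-protocol label, not the primary result. The variable needed for a true per-protocol set will already have been recorded under 6.3.3, but no analysis set draws on it.

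**Working it through.** There is no stated figure to reproduce. The check compares the definition with the rest of the protocol and then illustrates the scale.

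**1. Who is in the set as written**

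| Treatment through the pathway | Observed through Visit 3 | In the 10.3 per-protocol set? |
|---|---|---|
| As assigned | Yes | Yes |
| Not as assigned | Yes | Yes |
| As assigned | No | No |
| Not as assigned | No | No |

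Membership follows the second column only.

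**2. How it differs from intention to treat.** The intention-to-treat set holds all randomized children, and 10.4.2 imputes missing data. The 10.3 per-protocol set differs from it only by leaving out children with incomplete visits. Comparing the two probes the handling of missing data. It cannot probe treatment fidelity, because neither set conditions on treatment received.

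**3. Illustrative size.** The protocol gives no mismatch rate, so everything in this step is an assumption. Let p1 and p2 be the nonresponse rates under the two first-stage treatments, and let a share m of each arm receive the other arm's treatment in full.

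- Arm 1 shows (1 − m)p1 + m·p2.
- Arm 2 shows (1 − m)p2 + m·p1.
- The difference is (1 − 2m)(p1 − p2).

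For rates, take 36% and 24%. These are the ends of the range that Section 2.1 reports for new caries in earlier school trials. They are used here as hypothetical arm rates, not as a difference the trial expects.

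| Assumed m | Factor 1 − 2m | 12-point difference becomes |
|---|---|---|
| 2% | 0.96 | 12 × 0.96 = 11.5 points |
| 5% | 0.90 | 12 × 0.90 = 10.8 points |
| 10% | 0.80 | 12 × 0.80 = 9.6 points |

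At m = 5%, for example, the arms show 0.95 × 36 + 0.05 × 24 = 35.4% and 0.95 × 24 + 0.05 × 36 = 24.6%. If attendance is unrelated to mismatch, the same factor applies in the intention-to-treat set, so the 10.3 set removes none of the dilution.

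**4. Which treatments can count for which endpoint.** Section 7.3.3 lists the examination and response status at Visit 3 before second-stage randomization and treatment at that visit. Treatment given at Visit 3 therefore comes after the Visit 3 endpoint, and a per-protocol rule for that endpoint may use Visits 1 and 2 only. By the same order, the Visit 4 endpoint may use Visits 1 to 3, Visit 5 may use Visits 1 to 4, and Visit 6 may use Visits 1 to 5.

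**The case against.** The strongest reply is that nothing depends on this set. The primary analysis is by intention to treat, the trial tests superiority, and the protocol gives the per-protocol set no analysis, no robustness role and no decision. This stands, and it limits the weight of the point. A reader might infer that agreement between the two sets is meant to show robustness to non-compliance; the protocol never says so.

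A reader might also infer that 10.4.5 contradicts 6.3.3 by denying any adherence measure. The documents do not force that reading. The sentence in 10.4.5 gives clinician delivery as its reason, which points to participant adherence, and 6.3.3 likewise says that participant compliance is not assessed. On participants the two agree. What remains is loose wording, and no tabulation of the recorded clinician mismatches in 10.4.5.

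Third, the departures this protocol mainly expects are children leaving their schools (5.7.2, 10.4.5), and observation through Visit 3 matches the nonresponse window in 10.2. That makes a completer set a reasonable set to have. It does not make it per-protocol.

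Fourth, the factor 1 − 2m assumes full, symmetric switching. A real mismatch could be partial, such as one omitted component, and its frequency is unknown. This stands: the documents support no specific attenuation.

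Finally, a later analysis plan, due before database lock (10.1), could add criteria. But the complaint is not that a definition is missing. Section 10.3 states one, and it does not fit its label. In an open-label trial, fidelity criteria are better fixed before mismatches and outcomes are known.

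**Conclusion.** The point holds as a defect of definition. The per-protocol set in 10.3 is a completer set: it keeps children whose treatment did not match their assigned pathway, and it cannot inform on the effect of treatment received as assigned, although 6.3.3 records the information needed.

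The primary intention-to-treat conclusion is unaffected. The size of any attenuation within the set is unknown; the factor 1 − 2m rests wholly on an assumed share m and on full, symmetric switching. The point is worth correcting because the label would mislead and the correction is cheap, not because a result of the trial is shown to be wrong.

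**What to change.** In Section 10.3:

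- Rename the current set *completers through Visit 3*.
- Define per-protocol as randomized children observed through Visit 3 whose 6.3.3 comparison of health record and pathway shows the assigned first-stage treatment and, for those re-randomized before the endpoint being analysed, the assigned second-stage treatment.
- Count only treatment given before that endpoint's assessment: Visits 1 and 2 for the Visit 3 endpoint, and later visits correspondingly for Visits 4 to 6.
- Keep the requirement of observation through Visit 3. Without it, a correctly treated child seen only at baseline would qualify with no nonresponse outcome.
- Label the set supportive only, since it still selects on post-randomization events.

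In Section 10.4.5, state that the absence of an adherence measure refers to participants, and add a tabulation of the clinician mismatches from 6.3.3 by arm and stage.

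The cost is wording and a flag derived from data already recorded. No new data collection and no change to sample size or care are needed. The per-protocol set will be somewhat smaller than the completer set.
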